sonography within 21 days of study start reveals no evidence of follicular development in the face of a negative pregnancy test.

Visits 1 through 5 will occur during the first week of the study protocol. During Visits 1 through 4, subjects will undergo an HCG stimulation test (HCG-ST) in the CRC consisting of a single IM HCG injection during Visit 1 after documenting a negative urine pregnancy test, along with a single blood draw during all 4 visits at 0, 24, 48 and 96 hours after HCG administration to measure serum androgens and 17-hydroxyprogesterone. Visits 1 through 3 will be short lasting ~30 minutes. After one of these short visits, subjects will also undergo a body composition assessment consisting of a whole-body dual-emission X-ray absorptiometry (DEXA) scan in the Integrative Physiology Laboratory (IPL) at [name], and a magnetic resonance image of the abdomen in the Center for Magnetic Resonance Research at [name]. Visit 4 will last ~8 hours during which a cream challenge test (CCT) will also be performed in the CRC consisting of dairy cream ingestion and serial blood draws at 0, 2, 3 and 5 hours after cream ingestion to measure inflammation markers. Visit 5 will last ~7 hours and occur 2 days after the CCT during which subjects will undergo a FS-IVGTT in the CRC to assess insulin sensitivity and glucose-stimulated inflammation.

[figure not shown]
| Table 1. PRE-STUDY SCREENING | | | | |
|--|---------|---|---|---|
| STUDY PROTOCOL | WEEKS → | 0 | 4 | 8 |
| Salicylate Level | | X | X | X |
| Sex Hormone Binding Globulin | | X | | X |
| Body Composition: MRI & DEXA | | X | | |
| HCG Stimulation Test: T, A & 17OHP @ 0, 24, 48 & 96 hours. | | X | | X |
| Cream Challenge Test: MNC-derived ROS, NFκB, RNA & protein inflammat'n markers @ 0, 2, 3 & 5 hours. | | X | | X |
| Frequently Sampled Intravenous Glucose Tolerance Test: glucose, insulin, C-peptide & FFA q 1-30 minutes x 34 samples from -20-240 minutes. | | X | | X |
| Post-Study Safety Tests: CBC & CMP. | | | | X |
| Ovulation Monitoring: BBT from 0-12 weeks; P on 7th day of BBT rise; If P >2 ng/dl documented, vaginal sonography on day of & day after LH surge. | | | | |

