- **Ovulation Monitoring:** All subjects will maintain a basal body temperature (BBT) chart throughout the ~12 weeks of treatment after appropriate instructions. A blood sample (5 ml) will be drawn to measure serum progesterone to detect ovulation on the 7th day of temperature elevation of at least ¾°F from baseline indicative of a biphasic BBT response. Subjects will be instructed to alert the team regarding the potential need to schedule a progesterone measurement when 3 consecutive days of temperature elevation is evident. The length of the cycle in which a luteal range progesterone (>2 ng/ml) is documented will be used to time initiation of midcycle urine luteinizing hormone (LH) monitoring with a commercially available kit. Vaginal sonography will be performed in the CRC on the day of the color change signifying the LH surge and the following day to document follicular development and collapse, respectively, as the definitive evidence of ovulation.

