- **CCT, OGTT and HCG-ST** – The major risk associated with these tests is insertion of an intravenous catheter for blood drawing as discussed above. Glucose ingestion during the OGTT may cause abdominal discomfort, nausea, increased blood pressure, flushing or sweating. Dairy cream ingestion may cause urticaria, pruritus and in rare cases anaphylaxis in individuals with an unknown dairy allergy; and much less often may cause nausea, cramps, flatulence, bloating or diarrhea in individuals with previously unknown lactose intolerance.
- **FS-IVGTT** – The major risk of this test is hypoglycemia associated with the insulin infusion along with the risk associated with insertion of intravenous catheters for the infusions and blood drawing as discussed above. The frequent glucose measurements will allow prompt detection of hypoglycemia, in which case the test will be stopped and the intravenous glucose infusion will be increased or glucose will be given orally for resolution.
- **DEXA scans** involve a very small amount of radiation. One of the risks associated with radiation exposure is cancer. The natural incidence of fatal cancer in the U.S. is about 1 chance in 5. Everyday radiation exposure from natural occurring background radiation (sun, radon exposure in the home) is approximately 100 mrem (1 mSv) per year. Each subject in this study will receive a whole body DEXA scan. The radiation dose of one whole body DEXA scan is approximately ≤ 0.3 mrem. This amount of radiation is very low as to make an accurate risk estimate meaningless. A negative urine pregnancy test must be documented prior to undergoing the DEXA scan.
- **HCG Administration** – HCG use can cause the following adverse effects: edema, depression, fatigue, headache, irritability, restlessness, ovarian cyst rupture, reaction or pain at the injection site, or a local or systemic hypersensitivity reaction.

The risk of cyst rupture will be minimized by administering the HCG between days 3 and 13 following the onset of either a spontaneous or progestin-induced withdrawal bleed, or without regard to the onset of menses if vaginal sonography within 21 days of HCG administration reveals no evidence of follicle cyst development in the face of a negative pregnancy test.

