- **Salsalate Treatment** – Salsalate use can cause the following adverse effects characteristic of salicylates in descending order of frequency: tinnitus, nausea, hearing impairment, rash and vertigo. These effects are transient, and resolve upon cessation of salsalate. Although cause and effect has not been established, the following less common adverse effects have also been reported: abdominal pain, abnormal hepatic function, anaphylactic shock, angioedema, bronchospasm, decreased creatinine clearance, diarrhea, gastrointestinal irritation, inflammation, bleeding or perforation, hepatitis, hypotension, nephritis, urticaria, myocardial infarction or cerebral vascular accident.

Tinnitus is an expected side effect of salsalate treatment that occurs more frequently at doses higher than the one proposed for this study. To minimize this side effect, subjects will be advised to begin by taking one capsule (i.e. 500 mg of salsalate in subjects receiving salsalate) the first day and increase the dose in one capsule increments every 3 days thereafter until the desired dose is achieved. If tinnitus occurs at any point in the upward dose titration or later on during the treatment, an affected subject will be advised to reduce the daily study medication dose in stepped one capsule increments every 3 days. In a previous study, this approach effectively resolved symptoms enabling subjects to complete the study while still maintaining therapeutic salicylate levels. The nature of any suspicious symptoms reported by a subject will be reviewed to determine whether there is actual tinnitus before the salsalate dose is reduced in the manner described. Vital signs and potential side effects will be monitored every 4 weeks during treatment when subjects report to the CRC to have their blood draw for a salicylate level. Liver function tests, BUN and creatinine levels will be drawn within 4 weeks after study completion to be certain that no lasting untoward hepatic or renal impairment has occurred.

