This study is not powered to compare ovulation rates among the separate groups. Thus, ovulation rate post-treatment based on detection of luteal range progesterone elevations guided by BBTs will be compared between the salsalate and placebo groups overall. Based on the inclusion criteria, patients will be anovulatory pre-treatment, thus only post-treatment rates will be compared. With a sample size of 45 in each treatment group, if we expect approximately 10% to ovulate in the placebo arm, we will have over 80% power to detect a statistically significant difference if ovulation increases by 40% in the salsalate-treated group based on Fisher's exact test with type I error set at 0.05.

Aim 2: The primary outcome for Aim 2 is lipid-stimulated NF κ B EMSA density (i.e. change from baseline). The three contrasts of interest will be comparing the mean difference in lipid-stimulated NF κ B EMSA density between the salsalate and placebo group within each study group (i.e. salsalate-treated lean IR vs placebo lean IR, salsalate-treated lean non IR vs placebo lean non IR, and salsalate-treated obese vs placebo obese). Our preliminary baseline CCT data revealed similar results in women with PCOS and obese controls.¹¹ The lipid-stimulated NF κ B EMSA density in women with PCOS (n=17) compared with lean controls (n=8) revealed a mean ($\pm SD$) % change of 20.1 ± 10.4 vs. -3.0 ± 9.1 ($p<0.0001$, ES=1.9). The secondary outcomes for Aim 2 are glucose-stimulated NF κ B EMSA density and lipid-stimulated ROS generation (i.e. change from baseline). For women with PCOS compared with lean controls, our previously published baseline OGTT data showed a mean ($\pm SD$) % change of 34.6 ± 45.7 vs. -21.6 ± 35.6 ($p<0.04$, ES=1.4),¹³ and our baseline preliminary CCT data showed a mean ($\pm SD$) % change of 92 ± 38 vs. -7 ± 22 in ROS generation ($p<0.0001$, ES=3.8). For each of these outcomes, we will use a similar GLM framework as described in Aim 1 with the same three contrasts of interest. We will use a Sidak adjustment to control the type I error for each outcome. We expect post-salsalate treatment measures in PCOS will be similar to lean controls. Based on a two-sided two-sample t-test with a 0.017 α level to account for multiple comparisons which will yield similar power to our GLM model, we will have 80% power to detect an ES ≥ 1.24 . Thus, our study is sufficiently powered for these outcome measures.

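### Ovulation monitoring starts in the week of the baseline HCG test with no excluded window, so under the Section 12.2 definition a progesterone rise caused by the test could be counted as ovulation on treatment.

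*Combined protocol and SAP*

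**What the plan says.** Section 6.1 sets the monitoring period: "All subjects will maintain a basal body temperature (BBT) chart throughout the ~12 weeks of treatment after appropriate instructions". Table 1 in Section 6.0 gives it as weeks 0 to 12. Progesterone is drawn on the seventh day of a temperature rise of at least ¾°F, and Section 6.1 treats a value above 2 ng/ml as luteal range. The length of that cycle then decides when urine LH testing begins. Scans on the day of the surge and the next day look for follicular collapse, which Section 6.1 treats as conclusive.

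The baseline HCG test falls in the same first week. Section 6.0 has "a single IM HCG injection during Visit 1 after documenting a negative urine pregnancy test", and Section 6.1 gives the amount as 5,000 IU. Section 7.0 describes "administering the HCG between days 3 and 13 following the onset of either a spontaneous or progestin-induced withdrawal bleed". The alternative route allows entry at any time if a scan in the preceding 21 days showed no developing follicle and the pregnancy test is negative. That scan condition attaches only to the alternative route. Section 7.0 gives the purpose of the rule as limiting cyst rupture.

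Ovulation is defined in two ways. Section 12.2 uses luteal-range progesterone guided by BBT and says that "patients will be anovulatory pre-treatment, thus only post-treatment rates will be compared". Section 12.3 compares rates based on ultrasound evidence of follicular collapse. Neither section says which definition governs, or when counting starts relative to the HCG test.

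**The concern.** The HCG test is given because it stimulates the ovary. In a woman with a growing follicle it could plausibly bring on ovulation or luteinisation. If the resulting temperature and progesterone rise is picked up by monitoring, a product of the test enters the count of ovulations attributed to treatment, in either arm.

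Inducing ovulation is part of the main objective in Section 3.0, and the comparison is of on-treatment rates only, with no baseline rate to set against them. Events unrelated to treatment would bring the two rates closer together, so a real effect could be missed. The reported placebo rate would also be too high to serve later studies as a background rate.

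**Working it through.** **Timing.** Take the Visit 1 injection as day 0.
- The cream challenge is on the day of the 96-hour draw, which is day 4. The FS-IVGTT is two days later, so baseline testing ends at about day 4 + 2 = 6. Section 6.0 allows the test order to change, so this gap can be shorter.
- Assume the first raised temperature is on day 2 or 3 (the documents give no figure). The seventh raised day is then 2 + 6 = 8 or 3 + 6 = 9.
- The first dosing day is not stated. If dosing follows baseline testing, the progesterone draw falls in the first days of treatment.

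**The two definitions side by side.**
- Section 12.2: a value above 2 ng/ml on day 8 or 9 meets the definition, and nothing excludes it.
- Section 12.3: the same value is not the endpoint. Under Section 6.1, however, the length of that cycle times the LH testing and therefore the scans. A cycle altered by HCG could mistime them, and a later ovulation could be missed.

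**The plan's own power figure.** The inputs from Section 12.2 are:
- sample size: "With a sample size of 45 in each treatment group";
- placebo rate: "if we expect approximately 10% to ovulate in the placebo arm";
- an increase of 40% on salsalate;
- test: "based on Fisher's exact test with type I error set at 0.05". Sidedness is not stated, so two-sided is used here.

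Exact enumeration over all outcomes at 45 v 45 gives 98.7% for 10% v 50%, so the plan's claim of more than 80% holds if the 40% means percentage points. Read as a relative increase (10% v 14%), power is 4.8% and the claim is not reproduced.

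**Dilution.** Let h be the share of women in each arm with a test-caused event that is counted, equal in both arms and independent of true ovulation (assumptions). Then:

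observed rate = h + (1 − h) × true rate

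observed difference = (1 − h) × true difference

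For h = 0.1, placebo is 0.1 + 0.9 × 0.10 = 19% and salsalate is 0.1 + 0.9 × 0.50 = 55%, a difference of 0.9 × 40 = 36 points.

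| h (assumed) | Placebo | Salsalate | Difference (points) | Power |
|---|---|---|---|---|
| 0 | 10% | 50% | 40 | 98.7% |
| 0.1 | 19% | 55% | 36 | 93.3% |
| 0.2 | 28% | 60% | 32 | 82.0% |
| 0.3 | 37% | 65% | 28 | 68.3% |

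Power first falls below 80% at about h = 0.215. As a sensitivity check outside the plan's assumptions, a true salsalate rate of 40% gives 88.9% at h = 0 and falls below 80% at about h = 0.06.

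**Type I error.** With equal true rates of 10%, the exact rejection probability stays between 2.0% and 3.2% for h from 0 to 0.6. Equal contamination does not create false positives.

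**The case against.** Four points on the other side have weight.

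- **The analysis section may not count these events.** Section 12.3 uses follicular collapse, seen on scans timed by a later LH surge. A reader might infer from the monitoring rules that test-caused ovulations will be scored as treatment outcomes. The documents do not support that: it holds only if the Section 12.2 definition governs, and the plan does not settle which does. What remains under Section 12.3 is the possible mistiming of LH tests and scans.
- **Charting may start too late to see the rise.** If the chart begins with the first dose, at about day 6, temperature could already be raised. No low phase would be recorded and progesterone might never be drawn. Table 1's week 0 start permits charting from Visit 1 but does not establish it. The point is conditional on this.
- **The size is unsupported.** The women have oligo/amenorrhea, and Section 12.2 regards them as anovulatory before treatment. Entry is limited to days 3 to 13 or needs a scan showing no developing follicle. These rules make a large h harder to argue for, but they do not exclude such events, because women entering on days 3 to 13 need no such scan finding.
- **The outcome is not the primary one.** Section 12.2 names testosterone AUC as primary and S_I as secondary for Aim 1. That limits the consequences, although ovulation remains in the stated objective.

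A reader might also infer that early events should not count because women are told to "increase the dose in one capsule increments every 3 days thereafter until the desired dose is achieved". With one capsule on day 1, six capsules are reached on day 1 + 3 × 5 = 16 and eight on day 1 + 3 × 7 = 22. This is not a defect. Titration is part of the assigned regimen, and counting every event that occurs on it is a legitimate choice.

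**Conclusion.** The gap is real and limited. The plan does not say when ovulation counting starts relative to its own HCG test, and its two ovulation definitions give different answers on whether a test-caused rise counts. The possible harm is a difference reduced by the factor 1 − h and a raised placebo rate. On the reading that reproduces the plan's power claim, the loss is modest for small h and becomes material only above roughly one woman in five. That size rests on an assumed h, equal in both arms, on charting that covers the week of the injection, and on Section 12.2 supplying the definition. A false claim of benefit is not a reasonable inference. The point is worth correcting because the correction is cheap and ovulation is a stated objective.

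**What to change.** In Sections 6.1, 12.2 and 12.3:

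1. Reconcile the progesterone and ultrasound definitions so that one governs the compared rate and its power statement.
2. Count an ovulation only if its BBT rise starts after a single pre-specified interval following the Visit 1 HCG injection and before the Visit 8 injection. Fourteen days could serve as an example; the documents give no basis for a particular length, so state it as an assumption.
3. Do not use the length of the cycle containing the HCG injection to time LH monitoring.
4. Report earlier luteal-range progesterone values separately by arm, with a sensitivity analysis that includes them.

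Use one fixed interval, not a rule tied to the next bleed, which in women with infrequent cycles could remove far more observation time. The change is mainly to endpoint wording and uses data already collected. With 14 days, about two of the roughly 12 weeks are lost, so a few genuine early ovulations would go uncounted in both arms.

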A predefined computer-generated randomization schedule set up by a statistician will have centralized allocation and codes secured by a research pharmacist. This schedule will be used to assign recruited subjects to receive salsalate (Amneal Pharmaceuticals, Bridgewater, NJ) 3 grams/day (lean subjects) or 4 grams/day (obese subjects) in 2 divided doses or identical placebo for ~12 weeks. Study medication will actually be administered over a range of 11 to 13 weeks to accommodate scheduling glitches without impacting any anticipated treatment effects. Subjects and study personnel will be blinded to the treatment assignment. Serum salicylate levels will be measured to assess compliance from a fasting blood sample drawn at baseline (Visit 1) and after 4 weeks (Visit 6), 8 weeks (Visit 7) and 12 weeks (Visit 8) of treatment. Compliance will be defined as salicylate levels being in the therapeutic range for rheumatology practice (10-30 mg/dl) during treatment. A Data and Safety Monitoring Board (DSMB) will keep track of salicylate levels to maintain blinding (see Section 6.0). A fasting lipid profile will also be drawn at baseline (Visit 1) and after 12 weeks (Visit 8) of treatment.

During treatment, all subjects will undergo ovulation monitoring consisting of serum progesterone measurements timed by basal body temperatures along with serial follicular ultrasonography as indicated. After the ~12 weeks of treatment, subjects will undergo repeat testing consisting of an HCG-ST during Visit 8 through 11, a CCT during Visit 11 and a FS-

IVGTT during Visit 12. Visits 8 through 12 will occur during the last week of the study protocol. See Table 1 for an overview of the study protocol and Fig. 2 for the study timeline.

Figure 2

Although it is anticipated that the majority of subjects will undergo the three main test procedures (i.e. HCG-ST, CCT and FS-IVGTT) in the order described, the order in which they will be scheduled may need to be changed to accommodate scheduling glitches, since they will be performed as outpatient procedures in accordance with the CCTS CRC operating hours. The change in order will not impact the integrity of the data.

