12.3 Statistical Analysis

Initially, a full descriptive analysis of the data will be performed. Frequency distributions will be computed for all raw data and for change from baseline responses to lipid or glucose stimulation. Summary statistics will be provided by treatment group (salsalate, placebo) overall as well as by treatment group and study group (lean non-IR, lean IR, obese).

- i. Baseline data such as age, BMI, androgens, insulin sensitivity, total body fat and visceral fat will be compared between groups (salsalate: lean non-IR, lean IR, obese; placebo: lean non-IR, lean IR, obese) using analysis of variance (ANOVA) for normally distributed data or Kruskal-Wallis test for non-normal data to validate similarity of characteristics within each study group across the 2 treatment arms. If there is statistical significance, multiple comparisons between groups will be performed using a Sidak adjustment.
- ii. The primary outcome for Aim 1 is a difference in HCG-stimulated testosterone AUC between salsalate vs. placebo. To test our hypothesis, we will use a GLM framework with a dependent variable of post-treatment HCG-stimulated testosterone AUC including covariates for pre-treatment HCG-stimulated testosterone AUC, treatment indicator, study group (lean non-IR, lean IR, obese) and the treatment by study group interaction. Of primary interest will be the three contrasts of difference in mean between salsalate vs. placebo for these study groups. A Sidak adjustment will be used to control the Type I error. Analysis for the secondary measure of difference in S_i between salsalate and placebo for the insulin-resistant subjects only (lean IR, obese) will be compared using the same GLM framework, although only the overall contrast of difference in means between salsalate and placebo is of interest. Assumptions and model fit will be checked for all primary and secondary outcome analyses. Data will be transformed if necessary.

Post-treatment ovulation rates based on ultrasound documentation of follicular collapse will be compared between the salsalate-treated group and the placebo group using Fisher's exact test with type I error at 0.05. Also, ovulation rates and 95% exact confidence intervals will be estimated by study group (lean with IR, lean without IR, and obese) and treatment group.

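### If the section 12.3 definition governs, a follicle that ruptures after the single next-day scan is not counted as an ovulation in that cycle

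*Combined protocol and SAP*

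**What the plan says.** Under Ovulation Monitoring, section 6.1 sets two scans: "Vaginal sonography will be performed in the CRC on the day of the color change signifying the LH surge and the following day". Their purpose is "to document follicular development and collapse, respectively, as the definitive evidence of ovulation". The word 'respectively' gives the first scan to the follicle and the second to its collapse. Table 1 in section 6.0 names the same two days: "vaginal sonography on day of & day after LH surge".

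The text of section 6.0 speaks more loosely of progesterone timed by temperature charts "along with serial follicular ultrasonography as indicated", and section 3.0 uses similar words. Neither place gives a further scan day, a trigger for a repeat scan, or a rule for a follicle still intact on the second scan.

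Scanning is also conditional on an earlier result: "The length of the cycle in which a luteal range progesterone (>2 ng/ml) is documented will be used to time initiation" of the urine LH testing that triggers the scans.

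The two statistical sections define the endpoint differently. Section 12.3: "Post-treatment ovulation rates based on ultrasound documentation of follicular collapse will be compared between the salsalate-treated group and the placebo group". Section 12.2: "ovulation rate post-treatment based on detection of luteal range progesterone elevations guided by BBTs will be compared between the salsalate and placebo groups overall".

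**The concern.** Collapse cannot be recorded before it happens. With one scan assigned to it, on the day after the colour change, a later rupture leaves no record of collapse in that cycle. Read with section 12.3, that cycle yields no ovulation. The error runs one way: events are missed and none are added.

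The overall ovulation comparison is a planned Aim 1 test. Missed events would lower both arms' rates, shrink the absolute difference and cost power. The rates and exact confidence intervals that section 12.3 plans by study group and treatment would also be too low.

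**Working it through.** **Inputs from section 12.2.** 45 women per arm; placebo rate about 10%; an increase of 40% on salsalate; Fisher's exact test at 0.05; stated power above 80%. Sidedness is not given, so two-sided is assumed.

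**Reproducing the stated power.** With p0 and p1 the placebo and salsalate rates,

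power = sum over a, b = 0..45 of Bin(a; 45, p0) × Bin(b; 45, p1) × 1[Fisher p(a, b) ≤ 0.05].

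- 10% vs 50% (increase by 40 points): 98.7%
- 10% vs 40% (increase to 40%): 88.9%
- 10% vs 14% (relative increase): 4.8%

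Both absolute readings agree with the stated power; the relative reading does not. Each figure assumes that every ovulation is detected.

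**Adding missed collapses.** The documents give no interval from colour change to rupture, so the share s of ovulations with collapse visible on the next-day scan is an assumption. Take s equal in both arms, no false positives and one scanned cycle per woman. Then observed rate = s × true rate, and observed difference = s × (p1 − p0).

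| s | 10% vs 40% observed as | Power | 10% vs 50% observed as | Power |
|---|---|---|---|---|
| 1.0 | 10% vs 40% | 88.9% | 10% vs 50% | 98.7% |
| 0.9 | 9% vs 36% | 83.5% | 9% vs 45% | 97.0% |
| 0.8 | 8% vs 32% | 76.6% | 8% vs 40% | 93.9% |
| 0.6 | 6% vs 24% | 59.1% | 6% vs 30% | 81.2% |
| 0.5 | 5% vs 20% | 48.0% | 5% vs 25% | 70.8% |

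Power falls below 80% at s between 0.8 and 0.9 on the 40% reading, and between 0.5 and 0.6 on the 50% reading.

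**More than one scanned cycle.** Section 6.1 does not limit scanning to one cycle. With s = 0.5 per cycle and two independent scanned cycles, detection per woman is 1 − 0.5 × 0.5 = 0.75, and power is 72.6% or 91.7% instead of 48.0% or 70.8%.

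**Type I error.** If the true rates are equal at p, both observed rates equal s × p. The null hypothesis still holds for the observed data, and the test keeps its level.

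**Which definition.** In section 6.1 a scan follows only after a cycle with luteal-range progesterone. As written, every woman who reaches a scan has already met the section 12.2 definition. Under 12.2 the scan day cannot change her classification; under 12.3 it can.

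**The case against.** The strongest objection is that the stated power belongs to the progesterone definition in section 12.2, on which scan timing has no effect. A reader might infer from the table that the power claim is wrong or that the ovulation comparison is underpowered. The documents do not support that. The losses are conditional on section 12.3 governing and on a value of s that the documents do not give. On the 50% reading, power stays above 80% even with 40% of ovulations missed.

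A reader might also infer that one missed collapse makes a woman a non-ovulator for the whole trial. That does not follow, because she may be scanned in another cycle. Second chances may be few, though: treatment lasts about 12 weeks, the women are enrolled with infrequent or absent menses, and a progesterone-positive cycle must come first.

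The wording about serial ultrasonography leaves room for an extra scan. It sets no day or trigger, however, so it does not close the gap.

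Finally, ovulation is neither the primary outcome of Aim 1 (testosterone AUC) nor its named secondary (insulin sensitivity). That limits the weight of the point. It does not remove it, since the test is planned and has its own power statement.

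**Conclusion.** The point holds conditionally. If section 12.3 governs, the schedule in section 6.1 and Table 1 misses any rupture after the next-day scan in that cycle. Rates and exact confidence intervals are then biased low and power is lost, without inflation of type I error.

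The size cannot be fixed from the documents. With equal detection in both arms and one scanned cycle per woman, power is 76.6% or 93.9% at 80% detection and 48.0% or 70.8% at 50%, for 10% vs 40% and 10% vs 50% respectively. These are illustrations, not estimates of what this trial will lose. If section 12.2 governs, the effect on the comparison is nil. What the text shows without any assumption is that the two sections define ovulation differently, and that no rule covers a follicle still intact on the second scan.

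**What to change.** First, reconcile sections 12.2 and 12.3 on one definition of ovulation, and restate the power for that definition.

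If collapse is kept, move the second scan in section 6.1 and Table 1 from the day after the colour change to a later window. One starting about 48 hours after the colour change is an example; the sponsor should justify the choice and confirm that a collapse remains recognisable throughout the window. State that an intact follicle on an earlier scan is not scored as anovulation.

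The cost is a wording change in two places, with the same number of scans. The date of ovulation becomes less exact, but no planned analysis uses it.

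The change would not by itself secure the full-detection figures of 88.9% or 98.7%. A woman whose first progesterone-positive cycle comes late in the 12 weeks may never be scanned, and moving the second scan does not recover her. If collapse is the endpoint, the plan should also say how she is classified.
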